6.2 Other Secondary Outcomes (at all time periods see section 7)

- *Fatigue:* Bristol Rheumatoid Arthritis Fatigue Multi-Dimensional Questionnaire (BRAF-MDQ)⁶ assessing physical, living, cognition and emotional aspects of fatigue
- *Quality of life & health utility index:* SF-12⁷ assessing functional health and wellbeing from the patient's perspective
- *Pain:* Pain numerical rating scale (10 point) assessing pain intensity⁸
- Anxiety and depression: Hospital anxiety and depression scale (HADS)⁹
- *Sleep:* Sleep Problem Scale¹⁰
- *Impact on work:* Work Productivity and Activity Impairment Questionnaire: Specific Health Problem (WPAI:SHP)¹¹
- Impact on activities: Valued Life Activities Scale (short form S-VLA)¹²
- *Global outcome*: change of global health¹⁴

6.3 Additional Demographic and Mediator/moderator variables

- *Demographic:* Age, gender, marital status, employment status, level of education
- *Cognitions and behaviours:* Brief Illness Perception Questionnaire; Behavioural Response to Illness Questionnaire
- *Clinical:* Presence of fibromyalgia; Disease activity (self-reported)
- *Physical:* Physical activity profiles, over a 7 day period; Quantifying aerobic fitness (step) test (weight, VO₂ max and Borg Rating of Perceived Exertion)

6.4 Quantitative evaluation (Qualitative evaluation not covered here)

- Patient preference (only at baseline)
- Patient acceptability (assessed at week 28)

	ning	Proposed assessment [wks]			
	Scree	0	10	28	56
Demographic data					
Date of birth, gender, marital status, employment		~			
status, level of education					
Characteristics of study generalation					
Characteristics of study population					
Overall health (from domain in SF-12)		√			
Physical activity (typical self-reported)		√			
Experience of fatigue for more than 3 months	✓	✓			
Average level of fatigue(self reported- scale 1-10)	\checkmark	\checkmark			
Thyroid function test		\checkmark			
Urea and electrolytes		\checkmark			
Full blood count		✓			
Serological status ^s		\checkmark			
Erosive status		\checkmark			
Disease duration		\checkmark			
Presence of other co-morbidities		\checkmark	\checkmark	\checkmark	✓
(Charlson Index) ^D					
History of Suicide attempts		\checkmark			
Disease activity DAS28, ASDAS and BILAG for RA,		\checkmark	\checkmark	\checkmark	\checkmark
AxSpA and SLE respectively ^S					
Inflammation (CRP/ESR)		\checkmark	✓	✓	✓
Previous and current pharmacological therapies		\checkmark	\checkmark	\checkmark	\checkmark
Hypertension / Blood pressure ^S		\checkmark			

7 Timing of Outcome Measures

Primary Outcome					
Chalder Fatigue Scale (Likert scoring) D	~		✓	~	✓
Fatigue Severity Scale (FSS) D	~	1	\checkmark	\checkmark	\checkmark
Secondary Outcomes					
BRAF-MDQ (fatigue)	~	, ,	✓	✓	√
HADS (anxiety and depression)	~		√	✓	✓
Short Form-12 ^D	~		✓	✓	✓
Pain numerical rating scale ^D	~		✓	✓	✓
Sleep problem scale	•	/	\checkmark	\checkmark	\checkmark
Work Productivity and Activity Impairment	· ·	/	\checkmark	\checkmark	\checkmark
Questionnaire ^D					
Valued Life Activities Scale (short 14 items) D	~	/	\checkmark	\checkmark	\checkmark
Global outcome ^D			\checkmark	\checkmark	\checkmark
Additional mediator/moderator data					
Cognitions and behaviours		_			
Brief Illness Perception Questionnaire D	~		✓	✓	✓
Behavioural Response to Illness Questionnaire D	~	_	✓	\checkmark	✓
Clinical					
Procence of fibromyalgia D		/			✓
Disease estivity (self reported)		/	1	√	• •
Disease activity (self-reported)	· ·	_	•	•	v
Physical					
Physical activity profiles, over a 7 day period \$	•	/	\checkmark	\checkmark	\checkmark
Quantifying aerobic fitness (step) test (weight, VO ₂	~	/	\checkmark	\checkmark	\checkmark
max and Borg Rating of Perceived Exertion) \$					
Quantitative evaluation					
Patient preference	~	/			
Patient adherence (attendance records)	>	(x	x	
Patient engagement and adherence (telephone)			х	x	
Patient engagement and adherence (therapist view)			x	x	
Patient acceptability (Client Satisfaction				✓	
Questionnaire)					

S -Secondary analyses phase \$ PA summarised data to be threaded for the secondary analyses phase

D – derived variables

SAP ver

* For monitoring purpose only during the course of the trial - not in final analysis

the number of participants Lost to Follow-up (LTF) and/or who Discontinued the intervention will also be monitored along with reasonsrHCPs: rheumatology health care professionalsCBA: Cognitive Behavioural ApproachPEP: Personalised Exercise Programme

8 Trial Population

Patients with rheumatologist diagnosed IRDs (e.g. Rheumatoid Arthritis [RA], Systemic Lupus Erythematosus [SLE] and AxSpA, psoriatic arthritis, vasculitis or Sjogren's Syndrome).

9 Adverse events:

An adverse event (AE) is defined as any untoward medical occurrence in a participant, not necessarily being intervention related. Adverse events are collated according to the protocol (defined by the appropriate SOP). An adverse event is defined as "serious" (SAE) if it

- results in death
- is life threatening
- requires or prolongs inpatient hospitalisation
- results in persistent/significant disability/incapacity
- is otherwise considered medically significant by the investigator.

There are no related serious AEs expected in this trial. However, any serious related AEs that do occur will be recorded following specific Standard Operating Procedure (SOP) for adverse events in non-CTIMP studies. Hospitalisations for elective treatment of a pre-existing condition are not considered as an AE or SAE. Complications occurring during such hospitalisation are also not AEs or SAEs.

10 Sample Size and Power Calculation

Our planned primary Intention-to-Treat analyses (ITT) will compare PEP + usual care versus usual care alone, and CBA + usual care versus usual care alone. This was based on a standardised effect size of 0.50 (considered credible in other pragmatic effectiveness studies), which would equate to being powered to detect a minimal important clinical difference of 2 units in the CF Scale, assuming a common standard deviation across the randomised groups of 4 units, as with PACE ¹⁹. Assuming an overall significance level of 5% (by calculating the two pre-specified randomised groups comparisons, PEP + usual care vs. usual care alone and CBA + usual care vs usual care alone, at 2.5%, to maintain an overall level of not more than 5%) and a power of 90%, we require 100 evaluable participants in each of the three groups.

11 Statistical Methods

11.1 General Methods

All the main analyses will be based on the ITT principle and utilise all available follow-up data from all randomised participants who provide consent. Any post-randomisation exclusions will be removed. Final analysis will take place after full recruitment and follow-up. The results of the trial will follow the guidelines of the CONSORT statement developed specifically for social and psychological intervention trials ³ when presenting and analysing the data. Baseline characteristics of the study population will be summarised separately using the appropriate descriptive statistics and graphical summaries within each randomised group. Baseline characteristics will also be presented for dropouts and completers within each intervention group.

Treatment effects will be tested at the 2-sided 5% significance level with any estimates displayed with 95% confidence intervals (CIs) and p-values. There will be no

SAP version 1: LIFT

adjustment to secondary outcomes CIs for multiple testing. (See section 3 for statistician blinding)

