6.1 Primary Outcomes (Specifically at 56 weeks)

- Chalder Fatigue Scale (CF)¹⁶ assessing the physical and mental symptoms of fatigue as a total score using the Likert scale version and not as sub-domains
- Fatigue Severity Scale (FSS)¹⁷ assessing the impact of fatigue.

If the effect of intervention is positive on the CF, then the FSS outcome will be formally analysed. Should the intervention have no effect on the CF, then an explorative analysis of the FSS outcome will be performed.

(prior to 56 weeks these are also monitored and will be included in the final model but are considered as secondary outcomes)

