11.2 Statistical Analysis

LIFT has repeated measures on individual participants nested within site suggesting a multilevel model with an appropriate link function depending on the outcome. The analysis will adjust for the outcome variable at baseline as a covariate (when available) as well as the design factors also at baseline [diagnosis (RA, SLE, AxSpA or other IRD), the presence/absence of depressive symptoms HADS depression subscale >10)]. Centre clustering will be accounted for using a random effects robust variance.

11.2.1 Primary Outcome - Effectiveness Analysis.

We will test the primary hypothesis for between-group change in the primary outcome for each of the two pre-specified comparisons (CBA + usual care vs usual care alone and PEP + usual care vs usual care alone) using treatment and its interaction with time fitted as fixed effects, and we apply standard regression diagnostics. The main analysis will focus on the 56 weeks after baseline – providing effect sizes for each of the active arms compared to usual care. Standard regression diagnostics will be applied.

A Complier Average Causal Effect (CACE) analysis will be considered as a sensitivity analysis. Patent engagement & adherence (therapist view) at 8 weeks forms the CACE variable (if missing the 4 weeks reported value will be substituted) as a continuous instrumental variable in the CACE analysis

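### SAP 11.1 tests both primary comparisons at two-sided 5% although the trial was sized at 2.5% each, so the family-wise error is about 9% instead of the promised 5%

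*SAP*

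**What the plan says.** The sample size sections (Protocol 10.1 and SAP section 10, in near-identical terms) start from "Assuming an overall significance level of 5" per cent. They then carry out each of the two pre-specified comparisons "at 2.5%, to maintain an overall level of not more than 5" per cent. On that basis, with "a power of 90%, we require 100 evaluable participants in each of the three groups", the trial is "powered to detect a minimal important clinical difference of 2 units in the CF Scale", taking a standard deviation of 4 units.

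The analysis sections do not carry this through:

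- SAP 11.1 (General Methods) sets the only significance level in the methods: "Treatment effects will be tested at the 2-sided 5% significance level with any estimates displayed with 95% confidence intervals (CIs"). The one remark on multiplicity that follows concerns secondary outcomes, which are left unadjusted.
- SAP 11.2.1 announces the primary tests ("We will test the primary hypothesis for between-group change in the primary outcome for each of the two pre-specified comparisons") but gives no significance level.
- SAP 13.4, Table 8, the primary results shell, has 95% interval columns for both contrasts.
- Neither document names a Holm, Dunnett or hierarchical procedure between the two arms.
- The only gate runs from CF to FSS (Protocol 3.1, SAP 6.1, repeated under Table 8): "If the effect of intervention is positive on the CF, then the FSS outcome will be formally analysed". It gives no level for calling the effect positive, and it speaks of one intervention although there are two.

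**The concern.** The split of the significance level appears only where the sample size is justified. The section that will be programmed uses the full 5% for each contrast. The two rules disagree whenever a primary p-value lies between 0.025 and 0.05: section 11.1 calls that comparison a success and section 10 does not. The level therefore decides the headline result for each therapy. It also decides whether FSS, the second primary measure, is formally tested or only explored. If the conflict stays, the threshold could be settled after the results are known, and the overall 5% control stated in both documents would not hold.

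**Working it through.** **Inputs.** Difference 2 CF units, SD 4 (standardised effect 0.50), power 90%, two comparisons at 2.5% each, overall 5% (Protocol 10.1, SAP 10). Allocation 1:1:1 (SAP 3). Testing rule two-sided 5% (SAP 11.1). Sidedness is not stated in the sample size sections, so the first step checks it.

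**1. Reproduce the stated sample size.** Per arm, n = 2(z₁₋α/₂ + z_power)² / 0.50².

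- Two-sided 2.5%: 2(2.2414 + 1.2816)² / 0.25 = 99.3, rounded up to 100. This matches the plan.
- Two-sided 5%: 2(1.9600 + 1.2816)² / 0.25 = 84.1, rounded up to 85. This does not match, and neither does one-sided 2.5%, which is the same calculation.

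The trial was therefore sized for two-sided tests at 2.5%. Power at 100 per arm is 90.2% (normal approximation) or 89.8% (noncentral t).

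**2. Correlation of the two contrasts.** With equal arms and a common SD, each contrast has variance 2σ²/n, and the two share the usual-care mean with variance σ²/n. The correlation is (σ²/n) / (2σ²/n) = 0.5.

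**3. Family-wise error.** FWER = 1 − P(|Z₁| < c and |Z₂| < c), bivariate normal under both null hypotheses.

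| Correlation | Each at 5% (c = 1.960) | Each at 2.5% (c = 2.241) |
|---|---|---|
| 0 | 9.75% | 4.94% |
| 0.3 | 9.51% | 4.84% |
| 0.5 (this design) | **9.07%** | **4.65%** |
| 0.7 | 8.35% | 4.30% |

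A simulation of 2,000,000 draws with a shared control gave 9.07% and 4.66%. The upper bounds are 10% and 5%.

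**4. False claims of benefit only.** Counting rejections in the favourable direction alone, with correlation 0.5: 4.54% at two-sided 5% each, against 2.32% at two-sided 2.5% each.

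**5. Effect on the intervals.** For a simple two-group comparison, SE = 4 × √(2/100) = 0.566 units.

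- 95% half-width: 1.960 × 0.566 = 1.11 units.
- 97.5% half-width: 2.241 × 0.566 = 1.27 units.
- Ratio: 2.241 / 1.960 = 1.14, or about 14% wider.

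On these inputs, an observed CF difference between 1.11 and 1.27 units would succeed under SAP 11.1 and fail under SAP 10. The figures are illustrative, because the planned model also adjusts for baseline and uses repeated measures.

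**The case against.** The best defence is that the SAP still contains the split. Section 10 states it, section 12 refers the analyst to the protocol, and nothing withdraws it. The 5% sentence is under General Methods and names no outcome. Leaving secondary outcomes unadjusted could suggest that the primary ones are adjusted. On this reading the SAP contradicts itself but has not abandoned the 2.5% level. It is true that the split is not openly dropped, and the 9% arises only if section 11.1 governs the primary contrasts. But no methods section or table shell says that it does not. The reassuring reading has to be inferred, while the 5% rule is explicit.

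Three smaller points have some force:

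- The 9% counts errors in either direction. It is the right figure for the two-sided control that the plan promises. False claims of benefit alone are about half that, but they too roughly double, from 2.3% to 4.5%.
- Table 8 is a shell, and its interval columns also cover weeks 10 and 28, which SAP 6.1 treats as secondary. Relabelling the whole column would be wrong. Only the 56-week primary rows need to change.
- The unclear per-arm gate would exist at any significance level. It belongs here because the level chosen for CF is what opens the gate.

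One might also argue that two distinct treatments against a common control need no adjustment. Whatever the general merits, this trial committed to the adjustment in both documents and raised its requirement from 85 to 100 evaluable participants per arm to pay for it.

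**Conclusion.** The point holds and must be fixed. Under the SAP's only stated testing rule, the two-sided family-wise error for the two primary CF comparisons is 9.07%, against a stated maximum of 5%. Under the level used for sizing it is 4.65%. The 9.07% assumes equal arm sizes and a common SD (correlation 0.5) and that section 11.1 applies to the primary contrasts. No correlation from 0 to 0.7 brings it below 8.3%. The sample size itself is sound: 100 per arm reproduces at two-sided 2.5%.

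**What to change.** - **SAP 11.1 and 11.2.1:** state that each of the two CF contrasts at 56 weeks is tested at two-sided 2.5% and reported with a 97.5% interval.
- **SAP 6.1 and the note under Table 8:** apply the gate separately for each arm. FSS at 56 weeks is formally tested, at two-sided 2.5%, in an arm only if that arm's CF contrast has p < 0.025 in favour of the intervention. Otherwise FSS in that arm is exploratory. Each arm's CF-then-FSS sequence then uses at most 2.5%, and the two arms together at most 2.5% + 2.5% = 5%.
- **Table 8:** label the 56-week primary rows with 97.5% intervals. Keep 95% for weeks 10 and 28.
- **Secondary outcomes:** keep 5% and 95% intervals, unadjusted, as now.

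Another named procedure that controls the overall level at 5% would also resolve the conflict, but 2.5% each is what the sample size already provides for. The cost is SAP wording and table headers. Sample size, data collection and conduct do not change. Power stays at about 90%, and the primary intervals are about 14% wider than 95% intervals.

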11.2 Statistical Analysis

LIFT has repeated measures on individual participants nested within site suggesting a multilevel model with an appropriate link function depending on the outcome. The analysis will adjust for the outcome variable at baseline as a covariate (when available) as well as the design factors also at baseline [diagnosis (RA, SLE, AxSpA or other IRD), the presence/absence of depressive symptoms HADS depression subscale >10)]. Centre clustering will be accounted for using a random effects robust variance.

11.2.1 Primary Outcome - Effectiveness Analysis.

We will test the primary hypothesis for between-group change in the primary outcome for each of the two pre-specified comparisons (CBA + usual care vs usual care alone and PEP + usual care vs usual care alone) using treatment and its interaction with time fitted as fixed effects, and we apply standard regression diagnostics. The main analysis will focus on the 56 weeks after baseline – providing effect sizes for each of the active arms compared to usual care. Standard regression diagnostics will be applied.

A Complier Average Causal Effect (CACE) analysis will be considered as a sensitivity analysis. Patent engagement & adherence (therapist view) at 8 weeks forms the CACE variable (if missing the 4 weeks reported value will be substituted) as a continuous instrumental variable in the CACE analysis

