#### 10.2 Proposed Analysis

All statistical analyses will be governed by a comprehensive Statistical Analysis Plan, which will be authored by the study statistician and approved by the Trial Steering Committee and the Data Monitoring Committee before the main study outcome data are examined. All analyses will be carried out using Stata. In accordance with CONSORT guidelines, we will report all participant flow. Descriptive statistics of recruitment, drop-out and completeness of interventions will be provided.

Effectiveness Analysis: The main effectiveness analysis will be via intention-to-treat including all participants, with no planned interim analysis for early termination for either overwhelming evidence of effectiveness or abandoning for futility. Baseline characteristics will be presented by randomised group without formal statistical tests. We will test the primary hypothesis for between-group change in the primary outcome for each of the two pre-specified comparisons (CBA + usual care vs usual care alone and PEP + usual care vs usual care alone) using repeated measures mixed model, with subject as a random effect, and a suitably specified covariance structure (e.g. Autoregressive [1] (AR[1]), rheumatology healthcare professional as a random effect (to adjust for any clustering by rheumatology healthcare professional), with baseline outcome measure, and any other strongly predictive baseline measures, including the minimisation factors of presence/absence of depression and centre, and diagnosis. Treatment and its interaction with time will be fitted as fixed effects, and we apply standard regression diagnostics. The analysis will use statistical techniques for handling missing outcome data using multiple imputation under a missing at random (MAR) assumption. The secondary outcomes will be analysed using an analogous method. The main estimate of treatment effect will focus on the 56 weeks after baseline.

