After consent, participants will be randomised via Centre for Healthcare Randomised Trials (CHaRT) based within the University of Aberdeen. The CHaRT provides a 24 h randomisation web-based service. Using a computer-generated sequence, participants will be allocated to one of the two treatments or usual care (1:1:1 ratio).

Randomisation will be minimised by diagnosis (Rheumatic Arthritis [RA], Systemic Lupus Erythematosus [SLE], Axial Spondyloarthritis [AxSpA] or other Inflammatory Rheumatic Disease [IRD]) and the presence/absence of depressive symptoms (Hospital Anxiety & Depression Scale (HADS-D) depression subscale >10⁹ and will include a random element set at 20%. That is, 20% of all the allocated randomisations will be randomly re-allocated 50:50 to the remaining two treatment options.

Full blinding will not be possible due to the need to engage people in behavioural change. However, we will aim to blind research personnel undertaking outcome assessments to participants' treatment allocation – including the trial statistician with the data being analysed blind to allocation, until the final analyses.

4 Data Monitoring

While there are no planned interim analyses for efficacy or futility, an independent Data Monitoring Committee (DMC) will monitor trial progress and specifically any safety issues. The data available at each DMC will be preserved, along with all documentation of analysis plans, programming code and reporting provided.

For this relatively simple design, the biases should be minimal with the biggest threat being due to data missingness. However, to minimise bias:

- Only the DMC will see any data or analyses for their decisions making, prepared by the trial statistician (blinded –a colleague will re-run the code to reveal the true allocations for each interim report)
- The trial statistician will perform the final analyses, remaining blinded until the final follow-up and data entry has been completed

5 Timing of final Analyses

The final analyses will be performed after the last participants' final follow-up information has been collected and data entered.

6 Timing of Outcome Measurements

The outcome measurements have been planned be taken within a one-week period at defined times (10, 28 and 56 weeks) post randomisation. The actual times will be summarised in the results.

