13.4 Primary outcome summaries and model Estimates

Table 8: Primary outcome for Fatigue: Summaries*# and Model results

	CBA N =	PEP N=	Usual Care N =	Effect sizeª	95% CI	p- value	Effect size ^b	95% CI	p- value
Chalder Fatigue	Scale (Con	bined Liker	t score) 0-33 *c						
Baseline									
10wks									
28wks									
56wks (p)									
Fatigue Severity	/ Scale (FSS) *c							
Baseline									
10wks									
28wks									
56wks (^p)									
Baseline									
10wks									
28wks									
56wks (p)									

All models adjusted for their baseline outcome measure, HADS depression subscale >10 at baseline as fixed effects fixed effect with Centre clustering and individuals nested within centres as random effects *Continuous data:n; mean (sd), median (IQR) and (min, max)

Binary x/n (%)

^aMean difference between CBA and Usual care

^b Mean difference between PEP and Usual care

P Primary time point

^cMultilevel mixed-effects generalized linear model (glm) accounting for different time points.

Recall:

- The primary intention to treat analyses will compare PEP + usual care versus usual care alone, and CBA + usual care versus usual care giving effect sizes ^a and ^b
- The main estimate of treatment effect will focus on the 56 weeks after baseline.

- If the effect of intervention is positive on the CF, then the FSS outcome will be formally analysed. Should the intervention have no effect on the CF, then an explorative analysis of the FSS outcome will be performed.
- All analyses and reporting will follow the guidelines of the CONSORT statement developed specifically for social and psychological intervention trials ³
- CACE analysis as a sensitivity analysis will be considered for the primary outcome Chalder Fatigue

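### Minor free improvement: the outcome models use baseline depression only as HADS-D >10, and adding the full score already collected may gain a little precision

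*SAP*

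**What the plan says.** SAP 11.2 sets the covariates: "The analysis will adjust for the outcome variable at baseline as a covariate (when available) as well as the design factors also at baseline". The design factors are diagnosis and "the presence/absence of depressive symptoms HADS depression subscale >10". The Table 8 footnote repeats the cut: "All models adjusted for their baseline outcome measure, HADS depression subscale >10 at baseline as fixed effects". The Table 9 footnote does the same for the secondary outcomes. SAP 11.5 confirms that the models need nothing beyond the baseline outcome and the design factors.

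The cut comes from the allocation scheme. In Protocol 6.1 and SAP section 3, minimisation uses diagnosis and HADS-D >10, so a score of 10 counts as absent.

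The full HADS is collected at week 0 (Protocol 3.8, SAP section 7) and summarised as a continuous measure in SAP Table 3.

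Protocol 10.2 describes a wider covariate set than the SAP: "any other strongly predictive baseline measures, including the minimisation factors of presence/absence of depression and centre, and diagnosis". The SAP names no further predictor and does not say why that provision was left out.

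**The concern.** A yes/no factor treats a HADS-D of 0 and a HADS-D of 10 as the same, and likewise 11 and 21. If depression severity predicts fatigue at 56 weeks beyond what baseline fatigue and the cut already explain, that part stays in the residual variance and both primary confidence intervals are slightly wider than they could be. Minimisation balances the two categories but not severity within them, and the binary term cannot adjust for chance differences there.

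Only precision is at stake. The score is needed to allocate participants, so using it requires no new data.

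**Working it through.** **1. The plan's own figure.** Inputs from Protocol 10.1 and SAP section 10: difference 2, SD 4, 2.5% per comparison (taken as two-sided, as in SAP 11.1), power 90%.

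n = 2 × (2.2414 + 1.2816)² × 4² / 2² = 99.3, so 100 per group. Power at 100 is 90.2%. With 20% dropout, 100 / 0.8 = 125 per group, or 375 in all. The figure reproduces, and it takes no credit for any covariate.

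**2. Formula for the gain.** Scale the 56-week Chalder (CF) score to variance 1. Let r be the correlation of baseline with 56-week CF, a that of HADS-D with baseline CF, b that of HADS-D with 56-week CF, and p the share above the cut.

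- Residual variance given baseline CF and the score: V(a, b) = 1 − (r² + b² − 2rab) / (1 − a²).
- Given baseline CF and the binary factor: the same formula with ka and kb, where k = φ(c) / √(p(1 − p)) and c is the normal quantile for p. This gives k² = 0.49, 0.58 and 0.60 at p = 20%, 30% and 35%.
- Reduction in variance: 1 − V(a, b) / V(ka, kb). Under normality the factor adds nothing once the score is in, so score plus factor gives the same residual variance as score alone.

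**3. One case worked through.** Take p = 30%, r = 0.5, a = 0.5, b = 0.4. Then k = 0.759, ka = 0.379, kb = 0.303.

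- Binary: 1 − (0.250 + 0.092 − 0.115) / (1 − 0.144) = 0.735.
- Score: 1 − (0.25 + 0.16 − 0.20) / 0.75 = 0.720.
- Reduction: 1 − 0.720 / 0.735 = 2.0% of variance, or 1.0% of the standard error.

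With b = 0.3 instead, the two variances are 0.7483 and 0.7467: 0.2% of variance, 0.1% of the standard error.

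**4. Range.** None of r, a, b or p is given in the documents. Assumed: p 20–35%, r 0.4–0.5, a 0.4–0.6.

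| Assumed b | Fall in residual variance | Equivalent of 375 participants |
|---|---|---|
| 0.3 | 0 to 1.6% | 0 to 6 |
| 0.4 | 1.1 to 4.7% | 4 to 18 |
| 0.5 | 4.4 to 9.8% | 17 to 37 |

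The last column is the percentage times 375. The gain is exactly zero where b = ra, for example 0.3 = 0.5 × 0.6, because baseline CF then carries everything HADS-D could predict. Over an evenly spaced grid of 81 points with b from 0.3 to 0.4, the median fall is 1.4% (about 5 of 375), and about 35% of points reach 2%.

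**5. A second set of assumptions.** With p 20–40%, r 0.4–0.6, a 0.3–0.5 and b 0.2–0.5, the standard error falls by 0 to 5.7%, or 0 to 2.9% when b is at most 0.4. If the SD of 4 is read as the unadjusted SD, power at 100 per group rises by at most 1.6 points (1.0 when b is at most 0.4). If it is read as the residual SD, a 2%, 5% or 10% fall in variance moves power from 90.2% to 90.8%, 91.7% or 93.1%.

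**Limits.** The check treats the 56-week comparison as a single-time analysis of covariance with normal scores, and leaves out diagnosis and centre. FSS would follow the same formula with its own correlations, which are also not given.

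**The case against.** The strongest reply is that this is a preference, not a flaw. Adjusting for a minimisation factor in the form used at allocation is standard practice. Protocol 10.2 itself lists depression in present-or-absent form, so on depression the SAP does not depart from it. Nothing in the documents shows that HADS-D strongly predicts 56-week fatigue once baseline fatigue is in the model, so the condition in the protocol's provision is not shown to be met. The same argument could be made for baseline pain, sleep, illness perception or HADS anxiety. Chance imbalance in severity is random error already reflected in the confidence interval, not bias.

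All of that stands, and it limits the point to an optional improvement. HADS-D is still a reasonable first candidate, since the trial minimises on depression and must have the score to do so.

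A reader might also infer a large loss from the share of HADS-D's explained variance that a split keeps: 34%, 49% or 64% with 10%, 20% or 50% above the cut. That inference fails. Those shares apply when no other covariate is present, whereas every CF and FSS model also contains the baseline outcome. Only what HADS-D adds beyond baseline fatigue and the cut counts.

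**Conclusion.** This is a minor, free improvement. The SAP uses only the >10 factor although the full score is in hand, and it leaves out the protocol's provision for other predictive covariates without comment. Adding the score may narrow the primary intervals slightly: a 0 to 5% fall in residual variance for assumed correlations of 0.3 to 0.4 with 56-week CF, typically 1 to 2%, and up to about 10% at 0.5. At the low end the gain is nil.

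The documents do not support two stronger readings. One is that the binary adjustment is an error: it matches the minimisation, and the estimate and type I error are valid. The other is that the trial is underpowered because of it: the 100 per group assumes no covariate adjustment and is unaffected.

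**What to change.** Before unblinding, add to SAP 11.2 and to the Table 8 and 9 footnotes that the CF, FSS and other outcome models include the baseline HADS depression score as a continuous covariate, in addition to the >10 minimisation factor. For HADS-depression as an outcome no change is needed, since its baseline score is already in the model. If the team prefers not to add it, one sentence should say why the Protocol 10.2 provision for further predictive covariates was not carried into the SAP.

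The cost is one line of text, one model term and about one degree of freedom. It needs no new data and, if specified before unblinding, leaves type I error unchanged.
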